3.7.1 Schedule of Assessments

3.7.1.1 Visit 1 (Screening)

The screening period begins after consent is obtained and will take place between Day –35 and Day –8 prior to the initiation of the single-blind placebo run-in period. Completion of screening activities may require more than 1 visit. All procedures outlined for screening in the Schedule of Assessments ([Table 3.7-1](#)) will be performed. The following should also be noted:

- The investigator or his/her designee must obtain informed consent from the subject prior to any trial-related procedures being performed.
- A urine drug screen will be collected and sent to the central lab for evaluation. If subjects are taking disallowed medications and they are able to taper appropriately and safely, they will do so during the screening period. If medication taken is for ADHD, a minimum of 7 days off stimulants and 21 days off nonstimulants will be required before the single-blind placebo run-in period. A complete washout schedule, including common excluded medications and herbal preparations, is provided in [Section 4.1](#). A subject who tested positive for any prohibited medications at the screening visit must have a repeat urine drug screen that is confirmed as negative prior to performing Visit 2.
- An assessment of all inclusion and exclusion criteria will be made to determine the subject's eligibility for the trial.
- Medical and psychiatric history will be recorded, including the DSM-5 diagnosis of ADHD using the ACDS Version 1.2.
- Subjects will be administered the ASRS.
- A urine pregnancy test will be performed for all females of childbearing potential (FOCBP). If the urine pregnancy test is positive, the result should be confirmed with a serum pregnancy test. Subjects with a positive serum test result will be excluded from the trial.

External quality oversight methods will be used by Clinical Surveillance & Training (CST) to promote appropriate subject enrollment. Such methods will require sites to communicate certain aspects of subject data during the screening period to CST as detailed in the Operations Manual. Subjects cannot be randomized until approval from CST has been received. The investigator is responsible for ensuring that subjects are eligible for enrollment into the trial and for assessing subject safety throughout the trial.

Protocol 405-201-00014

3.7.1.2 Visit 2 (Single-blind Placebo Run-in)

After the subject has completed the medication washout period (if applicable), the Visit 2 (Day -7) assessments described in the Schedule of Assessments (Table 3.7-1) will be performed. The following should also be noted:

- Urine drug screen results from the previous visit will be reviewed. If the subject is positive for any prohibited medications at screening (including medications for the treatment of ADHD, see Section 4.1), and has not had a negative repeat urine drug screen confirmed since, the subject will be screen failed.
- Subjects will be administered the ASRS prior to the start of the single-blind placebo run-in period, and those with a $\geq 30\%$ improvement in the (18-item) ADHD Symptoms score compared to the score at screening will be screen failed, and not eligible for rescreening.
- All subjects must be unaware of the single-blind placebo run-in period so that it is indistinguishable from the double-blind treatment period. All subjects must be under the impression that they are starting to receive randomized treatment at the time of Visit 2 (Day -7).
- Placebo will be dispensed for the single-blind placebo run-in period, and subjects will be instructed to take their first dose from the dosing card in the clinic. Subjects will be instructed to take their doses at approximately the same time every day.
- The subject will download the AiCure Platform (Section 3.12) or receive a provisioned device with the AiCure Platform predownloaded, and will be trained on IMP compliance using this application.
- Subjects who discontinue the trial during the single-blind placebo run-in period should be considered early termination subjects, and should proceed with the early termination visit (Section 3.7.1.4.2) and follow-up procedures (Section 3.7.1.5 and Section 3.7.1.6).

3.7.1.3 Visit 3 (Baseline)

After the subject has completed the single-blind placebo run-in period, the Visit 3 (Day -1) assessments described in the Schedule of Assessments (Table 3.7-1) will be completed.

The following should also be noted:

- Urine drug screen results from the previous visit will be reviewed. If the subject is positive for any prohibited medications (including medications for the treatment of ADHD, see Section 4.1), the subject will be early terminated, and the procedures outlined in Section 3.7.1.4.2 will be completed.
- Subjects will be administered the ASRS, and those with a $\geq 30\%$ improvement in the (18-item) ADHD Symptoms score compared to the score at the start of single-blind placebo run-in will be early terminated.

Protocol 405-201-00014

- Subjects who do not meet eligibility (see Exclusion Criteria #30, #31, and #32) at the baseline visit are considered early termination subjects, and should proceed with the early termination visit (Section 3.7.1.4.2) and follow-up procedures (Section 3.7.1.5 and Section 3.7.1.6).
- Dosing cards from the single-blind run-in period will be returned; accountability and compliance will be verified.
- Blood samples for genotyping and for future biospecimen research (FBR) will be collected.
- Subjects entering the double-blind treatment period will be randomized (1:1:1) to receive centanafadine SR 200 mg TDD, 400 mg TDD, or placebo.
- Subjects will receive a dosing card for dosing on Days 1 to 7, and will be instructed to start dosing from the new card on the following day (Day 1), and to take their doses at approximately the same time every day.

3.7.1.4 Double-Blind Treatment Period

3.7.1.4.1 Visits 4 through 8

The assessments described for Visits 4 through 8 (Days 7-35) in the Schedule of Assessments (Table 3.7-1) will be completed. The following should also be noted:

- Urine drug screen results from the previous visit will be reviewed. If the subject is positive for any prohibited medications (including medications for the treatment of ADHD, see Section 4.1), the subject will be early terminated, and the procedures outlined in Section 3.7.1.4.2 will be completed.
- At each visit dosing cards from the prior week will be returned; accountability and compliance will be verified.
- Sparse PK samples will be collected at Visits 4 (Day 7), 5 (Day 14), and 7 (Day 28).
- Subjects will receive a dosing card for dosing at each visit for the next week, and will be instructed to start dosing from the new card on the following day, and to take their doses at approximately the same time every day.

3.7.1.4.2 Visit 9/End of Treatment/Early Termination

The assessments described for Visit 9 (Day 42/early termination [ET]) in the Schedule of Assessments (Table 3.7-1) will be completed. If a subject discontinues early before Day 42, procedures noted for Day 42 must be completed at the ET visit. Attempts should be made to complete ALL evaluations, particularly efficacy assessments (ie, AISRS, CGI Change from Baseline, CGI-S, ASRS, and AIM-A), for the Day 42/ET visit prior to the administration of any new ADHD medications. However, if the subject receives a new ADHD medication or has a urine drug screen positive for any new ADHD medication prior to the conduct of ET procedures, no efficacy assessments should be performed.

Protocol 405-201-00014

The following should also be noted:

- Urine drug screen results from the previous visit will be reviewed. If the subject is positive for any new ADHD medication, no efficacy assessments should be conducted.
- Subjects will return their dosing card from the prior week, accountability, and compliance will be verified.
- Sparse PK sample will be collected.
- For all subjects who complete the trial (Section 3.10) and are considering entry into the open-label rollover trial, they will be instructed to refrain from utilizing prohibited concomitant medications (Section 4.1), including ADHD treatments, during the 7-day safety follow-up period. For subjects who early terminate or decline participation in the open-label trial, they will be instructed to refrain from utilizing prohibited concomitant medications (Section 4.1), including ADHD treatments, until after the follow-up telephone call 10 days after the last dose of IMP.
- For subjects who early terminate or decline participation in the open-label trial, future treatment options will be discussed, and subjects will complete follow-up visits and procedures described in Section 3.7.1.5 and Section 3.7.1.6.

3.7.1.5 Visits 10 Through 14 (Follow-up)

All subjects, whether they complete the trial or are withdrawn prematurely for any reason, will be followed up for a safety evaluation for 7 days (follow-up telephone calls at 1, 3, and 5 days after the last dose of IMP, and in-clinic visits 2 and 7 days after the last dose of IMP). The assessments described in the Follow-up Schedule of Assessments (Table 3.7-2) will be completed. The following should also be noted:

Subjects who complete both the 6-week double-blind treatment period, the 7-day follow-up period (follow-up telephone calls at 1, 3, and 5 days after the last dose of IMP, and in-clinic visits 2 and 7 days after the last dose of IMP), and who refrain from using prohibited medications (Section 4.1) after the IMP is stopped, may be eligible to enroll into Trial 405-201-00015, which is a 12-month, observational, open-label trial to evaluate the long-term safety and tolerability of subjects with ADHD who previously participated in Trials 405-201-00013 or 405-201-00014. For subjects who early terminate or decline participation in the open-label trial, they will be instructed to refrain from utilizing prohibited concomitant medications (Section 4.1), including ADHD treatments, until after the follow-up telephone call 10 days after the last dose of IMP (Section 3.7.1.6). Subjects who will be rolling over into the open-label trial will need to sign the Trial 405-201-00015 informed consent form prior to activities performed at the 7-day follow-up visit of Trial 405-201-00014.

Protocol 405-201-00014

3.7.1.6 Visit 15 (Follow-up)

Subjects who terminate early, decide to not enroll in Trial 405-201-00015, or who are not eligible to enroll in Trial 405-201-00015, will be required to participate in an additional follow-up via telephone call 10 days after the last dose of IMP. For subjects who early terminate or decline participation in the open-label trial, they will be instructed to refrain from utilizing prohibited concomitant medications (Section 4.1), including ADHD treatments, until after the follow-up telephone call 10 days after the last dose of IMP. The assessments described in the Follow-up Schedule of Assessments (Table 3.7-2) will be completed.

3.7.2 Efficacy Assessments

It is required that adequately trained and experienced clinicians administer the ACDS, MINI, AISRS, CGI-S, and CGI Change from Baseline. All individuals performing these assessments must be pre-approved by the sponsor or designee.

3.7.2.1 Adult Attention-deficit/Hyperactivity Disorder Investigator Symptom Rating Scale

The AISRS is a modified version of the ADHD Rating Scale that reflects the impact and severity of ADHD among adults, and will be administered as described in the Schedule of Assessments (Table 3.7-1 and Table 3.7-2). It is a clinician-administered scale that measures the 18 symptoms of adult ADHD using a Likert scale: 0 (none); 1 (mild); 2 (moderate); and 3 (severe), and uses a semi-structured interview methodology with suggested prompts for each item to improve interrater reliability. The scale's 18 items directly correspond to the 18 DSM-5 symptoms of ADHD where 9 inattentive items alternate with 9 hyperactive impulsive items. The maximum total score for the scale is 54 points, with 27 points for each subscale. The total score is the sum of both the Inattentive and Hyperactive Impulsive subscales.²⁷

3.7.2.2 Clinical Global Impression-Severity of Illness Scale - Modified for Attention-deficit/Hyperactivity Disorder

The CGI-S modified (Table 3.7-1) is an observer-rated scale that will be used to measure symptom severity.²⁸ To perform this assessment, the investigator or rater will respond to the following question: "Considering your total clinical experience with adult ADHD, how mentally ill is the patient at this time?" Response choices include: 1 = normal, not at all ill; 2 = borderline mentally ill; 3 = mildly ill; 4 = moderately ill; 5 = markedly ill; 6 = severely ill; and 7 = among the most extremely ill patients.²⁹

Protocol 405-201-00014

3.7.2.3 Clinical Global Impression Change from Baseline

The CGI Change from Baseline (Table 3.7-1) is an observer-rated scale that will be used to measure the subject's total improvement compared to before trial drug treatment was initiated.²⁸ The rater or investigator will rate the subject's total improvement relative to baseline. Response choices include: 1 = very much improved, 2 = much improved, 3 = minimally improved, 4 = no change, 5 = minimally worse, 6 = much worse, and 7 = very much worse.²⁹

3.7.3 Other Assessments

3.7.3.1 Mini International Neuropsychiatric Interview

The MINI^{30,31,32} will be conducted as outlined in the Schedule of Assessments (Table 3.7-1) to rule out exclusionary comorbid psychiatric diagnoses. Detailed instructions for administration of this structured interview will be provided.

3.7.3.2 Adult ADHD Clinical Diagnostic Scale

The ACDS Version 1.2 (Table 3.7-1) is a clinician-administered, semistructured interview assessment used to establish the presence of current adult symptoms of ADHD, with suggested age-specific prompts for rating both childhood and adult symptoms. The ACDS includes a retrospective assessment of all childhood ADHD symptoms as well as an assessment of recent (last 6 months) adult ADHD symptoms that includes 9 criterion symptoms of inattention, 9 criterion symptoms of hyperactivity and impulsivity, and 14 non-DSM symptoms believed to be relevant to adult ADHD.³³

3.7.3.3 Attention-deficit/Hyperactivity Disorder Impact Module - Adult

The AIM-A (Table 3.7-1) is a subject self-report questionnaire which assesses quality of life in adults with ADHD. The questionnaire has 4 global quality of life items, 5 economic impact items, and 5 multi-item scales that assess the following key concepts: Living with ADHD, General Well-Being, Work, Home and School Performance and Daily Functioning. Additionally, Relationships and Communication, and Impact of Symptoms are also included.³⁴

Protocol 405-201-00014

3.7.3.4 Adult Attention-deficit/Hyperactivity Disorder Self-Report Scale, Expanded Version

The ASRS Version 1.1, ([Table 3.7-1](#)) is a self-report questionnaire developed by the WHO. The subject will answer 31 questions. Of those 31, 18 of the questions pertain to the 18 DSM-5 ADHD symptoms (ADHD Symptoms). The expanded version includes 9 additional items that assess Executive Function Deficits, and 4 items that assess Emotional Dyscontrol.³⁵

3.7.4 Prior and Concomitant Medications

The investigator will record all medications and therapies taken by the subject from 30 days prior to signing of informed consent through the end of the evaluation period (defined as the time period during which subjects are evaluated for primary and secondary objectives) on the eCRF. Details of prohibited and restricted medications are provided in [Section 4.1](#). The investigator will record all medications and therapies taken by the subject for treatment of an AE or which caused an AE until the end of the trial (defined as the last date of contact or date of final contact attempt) on the eCRF.

3.7.5 Safety Assessments

3.7.5.1 Adverse Events

Refer to [Section 5](#).

3.7.5.2 Clinical Laboratory Assessments

A central laboratory designated by the sponsor will be used for all laboratory testing required during the trial. The central laboratory should be used for all laboratory testing whenever possible (including unscheduled and follow up, if needed). In cases where an immediate result is required for a particular laboratory test, the sample should be divided and sent to both a local laboratory and the designated central laboratory. Urine will be collected and blood will be drawn from each subject during screening prior to treatment with the IMP. Subjects should be fasting for a minimum of 8 hours prior to the blood draws, if possible. If fasting blood samples are not feasible at screening, nonfasting blood samples may be obtained initially for determining eligibility for the trial. If a fasting blood sample was obtained at the screening visit and less than 14 days have elapsed since the screening visit, clinical laboratory tests (hematology, serum chemistry, and urinalysis) do not need to be repeated at the baseline visit. The results of these tests must be reviewed by the investigator prior to initiation of the administration of the IMP. Clinical laboratory tests at other visits should be drawn fasting, if possible, but must be drawn after a minimum 8-hour fast at Day 42/ET. All blood collections must occur after the

Protocol 405-201-00014

administration of efficacy assessments and safety assessments (eg, AE monitoring, physical examination, vital sign measurements, ECGs, medication withdrawal scales, and suicidality) at any given visit. See exclusion criteria (Section 3.4.3) based on screening laboratory tests. Additional urine and blood samples may be collected for further evaluation of safety as warranted by the investigator’s judgment. Reports from the central laboratory will be retained electronically within the laboratory vendor’s online portal and assessed by the investigator or qualified designee for clinical significance within the eCRF.

Table 3.7.5.2-1 Clinical Laboratory Assessments	

Hematology: Hematocrit Hemoglobin Mean corpuscular hemoglobin concentration Mean corpuscular hemoglobin Mean corpuscular volume Platelet count RBC count WBC count with differential
 
Urinalysis: Color Bilirubin Blood Glucose Ketones Leukocyte esterase Microscopic analysis, WBC/RBC counts per high powered field Nitrite pH Protein Specific gravity Urobilinogen
 
Urine Drug Screen Amphetamines Barbiturates Benzodiazepines Cannabinoids Cocaine Marijuana Methadone Methylphenidate (ritalinic acid) Opiates Phencyclidine Propoxyphene
 
Other Alcohol testing via breathalyzer or blood
	
Serum Chemistry: Albumin Alkaline phosphatase ALT AST Bicarbonate Bilirubin, total Blood urea nitrogen Calcium Cholesterol (total, HDL, LDL) Chloride CPK Creatinine Gamma glutamyl transferase Glucose Magnesium Potassium Phosphorus Protein, total Sodium Triglycerides Uric acid
 
Additional Tests: Urine pregnancy (FOCBP), serum test will confirm positive urine test results PT and INR (screening, baseline, and Day 42/ET) CPK reflex for isoenzymes if CPK > 3 × ULN; serum and urine myoglobin collected if CPK > 5 × ULN
 
Additional Tests (Screening Only) HBsAg Anti-HCV HIV TSH, with reflex to free T4 if TSH is abnormal HbA1c

Protocol 405-201-00014

CPK = creatine phosphokinase; HDL = high-density lipoprotein; INR = international normalized ratio; LDL = low-density lipoprotein; PT = prothrombin time; RBC = red blood cell; ULN = upper limit of normal; WBC = white blood cell.

The total volume of blood to be collected during the trial will be documented in the eICF.

Any value outside the normal range will be flagged for the attention of the investigator who must indicate whether or not a flagged value is of clinical significance. If one or more values are questionable, the test(s) may be repeated. If the result of any test (or repeat test, if done) is indicated as clinically significant in the samples taken during the screening period, the subject will NOT be enrolled into the trial without the permission of the medical monitor. In addition, unscheduled laboratory tests should be performed if clinically significant abnormalities are observed. Unscheduled laboratory tests may be repeated at any time at the discretion of the investigator for appropriate medical care. Refer to [Appendix 2](#) for criteria for identifying values of potential clinical relevance.

A pregnancy test will be conducted in all FOCBP prior to trial intervention; results must be available prior to the administration of the IMP. All positive urine pregnancy test results must be confirmed by a serum test. Subjects with a positive serum pregnancy test result at screening must not be enrolled. Subjects with a positive serum pregnancy test result during the trial must discontinue treatment and be withdrawn from the trial. Pregnancy tests will be performed in FOCBP at each visit during the trial. An additional pregnancy test will be conducted in FOCBP at the Day 42/ET visit.

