7.1 Baseline Definition

Baseline for the single-blind placebo run-in period refers to last available measurement prior to the start of administration of placebo in the single-blind placebo run-in period.

For analyses of the double-blind treatment period data, the baseline is defined as the last available measurement prior to the first dose of double-blind Investigational Medicinal Product (IMP) in the double-blind treatment period.

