9.2 Clinical Laboratory Tests

Summary statistics for routine clinical laboratory measurements will be provided. For The double-blind treatment period laboratory tests, change from baseline for the double-blind

SAP 405-201-00014

treatment period will be summarized by treatment group. Potentially clinically relevant results in laboratory tests will also be summarized.

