Appendix 2 Criteria for Identifying Laboratory Values of Potential Clinical Relevance

Laboratory Tests	Criteria
Chemistry	
AST (SGOT)	≥ 3 x upper limit of normal (ULN)
ALT (SGPT)	≥ 3 x ULN
Alkaline phosphatase	≥ 3 x ULN
BUN	≥ 30 mg/dL
Creatinine	≥ 2.0 mg/dL
Uric Acid	
Men	≥ 10.5 mg/dL
Women	≥ 8.5 mg/dL
Bilirubin (total)	≥ 2.0 mg/dL
Creatine Phosphokinase (CPK)	> 3 x ULN
Hematology	
Hematocrit	
Men	≤ 37 % and decrease of ≥ 3 percentage points from Baseline
Women	≤ 32 % and decrease of ≥ 3 percentage points from Baseline
Hemoglobin	
Men	≤ 11.5 g/dL
Women	≤ 9.5 g/dL
White blood count	≤ 2,800/ mm ³ or ≥ 16,000/ mm ³
Eosinophils	≥ 10%
Neutrophils	≤ 15%
Absolute neutrophil count	≤ 1,500/ mm ³
Platelet count	≤ 75,000/ mm ³ or ≥ 700,000/ mm ³
Urinalysis	
Protein	Increase of ≥ 2 units
Glucose	Increase of ≥ 2 units
Additional Criteria	
Chloride	≤ 90 mEq/L or ≥ 118 mEq/L
Potassium	≤ 2.5 mEq/L or ≥ 6.5 mEq/L
Sodium	≤ 126 mEq/L or ≥ 156 mEq/L
Calcium	≤ 8.2 mg/dL or ≥ 12 mg/dL
Glucose	
Fasting	≥ 100 mg/dL
Non-Fasting	≥ 200 mg/dL
Total Cholesterol, Fasting	≥ 240 mg/dL
LDL Cholesterol, Fasting	≥ 160 mg/dL
HDL Cholesterol, Fasting	
Men	< 40 mg/dL
Women	< 50 mg/dL
Triglycerides, Fasting	≥ 150 mg/dL

SAP 405-201-00014

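### Within-arm glucose and lipid changes to Day 42/ET can set a nonfasting baseline against a mandatory fasting sample, and the SAP's mean-change summary takes no account of fasting status

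*Protocol*

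**What the plan says.** Protocol 3.7.5.2 sets the general rule: "Subjects should be fasting for a minimum of 8 hours prior to the blood draws, if possible". At screening, where fasting is not feasible, "nonfasting blood samples may be obtained initially for determining eligibility for the trial". The baseline draw may be skipped on one condition: "If a fasting blood sample was obtained at the screening visit and less than 14 days have elapsed since the screening visit". For the remaining visits, "Clinical laboratory tests at other visits should be drawn fasting, if possible", but at the end of treatment samples "must be drawn after a minimum 8-hour fast at Day 42/ET".

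On the analysis side, SAP 7.1 states that for the double-blind period "the baseline is defined as the last available measurement prior to the first dose of double-blind Investigational Medicinal Product". It sets no fasting condition. The operative words in SAP 9.2 are "laboratory tests, change from baseline for the double-blind" treatment period, to be summarised by treatment group; fasting is not mentioned. The planned display for serum chemistry, CT-10.2.3.1, has no fasting split in its title. Protocol Table 3.7.5.2-1 places glucose, total, HDL and LDL cholesterol and triglycerides under serum chemistry.

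The plan does treat fasting as material elsewhere. SAP Appendix 2 gives glucose two limits (fasting ≥ 100 mg/dL, nonfasting ≥ 200 mg/dL) and words its lipid limits for fasting samples only, as in the row labelled "Triglycerides, Fasting".

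**The concern.** A change from baseline should compare like with like. Here one end of the comparison has an enforced fast and the other does not. For any subject whose baseline was nonfasting, the computed change in glucose or a lipid contains the difference between a fed and a fasted sample, on top of whatever treatment or time did.

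What is at stake is how the mean-change table reads within an arm. SAP 9.2 plans summary statistics by arm and states no between-arm test for laboratory values, whereas SAP 9.5.1 gives body weight an ANCOVA. Someone reading an arm's own mean change in triglycerides to Day 42/ET could take a sampling artefact for an effect, or the reverse.

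**Working it through.** The plan states no figure on this point, so there is nothing to reproduce. The check has three parts.

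**1. Fasting rule at each scheduled laboratory draw** (visits from Protocol Table 3.7-1, rules from Protocol 3.7.5.2)

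| Draw | Fasting |
|---|---|
| Screening | If feasible; nonfasting accepted at first, for eligibility |
| Visit 2 (Day −7) | If feasible |
| Baseline (Day −1) | If feasible; may be skipped after a fasting screening sample under 14 days old |
| Day 14 | If feasible |
| Day 42/ET | Mandatory, at least 8 hours |

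**2. Which sample becomes the SAP baseline**

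- Screening sample nonfasting: the waiver does not apply, so a baseline draw is due, fasting if feasible.
- Screening sample fasting but 14 or more days old: the same.
- Screening sample fasting and under 14 days old: the baseline draw may be skipped. Visit 2 tests are still scheduled, so under SAP 7.1 a nonfasting Visit 2 value would displace the fasting screening value as the last one before dosing.

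A nonfasting baseline is therefore possible on every path, although the protocol leans against it.

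**3. Size**

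Let *f* be the share of an arm with a nonfasting baseline, and *d* the mean nonfasting minus fasting value of the analyte. If all Day 42/ET samples are fasting:

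shift in that arm's mean change = −*f* × *d*

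Both *f* and *d* are assumptions; the documents give neither. Results in mg/dL:

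| *d* | *f* = 0 | *f* = 10% | *f* = 25% | *f* = 50% |
|---|---|---|---|---|
| −10 | 0 | +1.0 | +2.5 | +5.0 |
| 0 | 0 | 0 | 0 | 0 |
| +10 | 0 | −1.0 | −2.5 | −5.0 |
| +20 | 0 | −2.0 | −5.0 | −10.0 |
| +50 | 0 | −5.0 | −12.5 | −25.0 |

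For the contrast between arms:

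shift in active minus placebo = −*d* × (*f*<sub>active</sub> − *f*<sub>placebo</sub>)

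Randomisation makes the expected value of this 0. Chance imbalance has standard deviation |*d*| × √(2*f*(1 − *f*)/*n*). With the planned *n* = 150 per arm and *f* = 50%, √(2 × 0.5 × 0.5/150) = 0.0577. That gives 0.58 mg/dL for *d* = 10, 1.15 for *d* = 20 and 2.89 for *d* = 50.

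**The case against.** The case for leaving the plan alone has four parts, and each stands as a limit on the point.

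- The protocol steers toward a fasting baseline. A nonfasting screening sample never excuses the baseline draw, and every draw is to be fasting if feasible. The share *f* may be small or zero.
- The safety objective is a comparison with placebo (Protocol 2.3). Baseline fasting status is settled before double-blind dosing, so any shift is expected to be the same in all arms.
- Fasting is not ignored throughout. SAP 9.2.1 and tables CT-10.2.1.1, CT-10.2.1.2 and CT-10.2.2 list and count values of potential clinical relevance. For glucose and lipids these limits are absolute and fasting-specific, with no baseline term. A fasting Day 42 triglyceride of 150 mg/dL or more is counted whatever the baseline sample was.
- Baseline and Day 14 share the same permissive rule, so the asymmetry does not apply to the Day 14 change.

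None of this makes the mean-change column to Day 42/ET a like-for-like comparison within an arm. The plan already needs fasting status to apply Appendix 2, so leaving it out of the adjacent table gains nothing.

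**Conclusion.** A cheap improvement. Baseline samples may be nonfasting, Day 42/ET samples must be fasting, and the mean-change summary differences them without regard to that. Within-arm changes in glucose and lipids to Day 42/ET can therefore mix a fed-to-fasting shift with treatment or time effects. The size is −*f* × *d*, with both terms unknown.

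A reader might infer two stronger things, and the documents support neither.

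- **That glucose and all lipid changes are biased downward in every arm.** This needs *f* > 0 and *d* > 0 for each analyte. The only hint of direction is the pair of glucose limits in Appendix 2. Nothing in the documents gives a sign for triglycerides or for total, LDL or HDL cholesterol.
- **That a drug-related rise would be hidden.** The shift is expected to be equal across arms, so such a rise would still appear as a difference from placebo. That contrast is unbiased in expectation, with some added noise.

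The statement about the contrast assumes that the Day 42/ET fast is kept alike in all arms and that having a Day 42/ET sample does not depend on baseline fasting status differently by arm.

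**What to change.** In SAP 9.2, base the change-from-baseline summaries of glucose, total, LDL and HDL cholesterol and triglycerides on subjects with fasting samples at both time points. Show the all-sample values as a secondary row.

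Do not replace a nonfasting baseline with an older screening sample. Screening runs from Day −35 to Day −8 and contains the medication washout (Protocol 3.7.1.1), so such a sample may precede washout, and it departs from the baseline in SAP 7.1. At most, allow a fasting screening sample less than 14 days old, which Protocol 3.7.5.2 already accepts in place of the baseline repeat. If that is done, the SAP should say so, because it also settles the case where a nonfasting Visit 2 value would otherwise be taken.

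The cost is a sentence in the SAP, a filter on fasting status, and fewer subjects for five analytes in a descriptive table. No visit procedure, efficacy analysis or sample size changes.
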